10.4.2.8.5 Completing the Measures

1. When the participant finishes viewing the slides study personnel should meet with her to review the instructions and answer any procedural questions she might have regarding either the Voiding Diary or the Pad Test.
2. Then, using the participant's calendar, identify the time of her next menstrual period and determine the appropriate dates and days to complete the Voiding Diary, the Pad Test, and next study visit. Write the start day of the diary and the start day of the Pad Test on the Pad Test Reminder insert and place it in the Pad Test Kit. Review the contents of the Kit with the participant.
3. Next, the study nurse gives the participant the Pad Test Kit, prepared to the participant's personal specifications and gives the participant the clinic telephone number, encouraging her to call with any question or concerns.
4. As a reminder, the study nurse should make arrangements to contact the participant one day prior to the start of the Voiding Diary to remind her to complete the Diary and Pad Test as planned. The nurse should schedule with the participant a convenient time to talk for the reminder call. This will provide a good opportunity for the nurse to answer any final questions the participant might have prior to the start of the measures.

10.4.2.8.6 Recording the Data

When the participant returns with the completed Voiding Diary and the Pad Test Kit (including all used and unused pads) the study nurse weighs each of the Pads in the Kit per protocol and completes all the remaining sections of the Pad Test data form at that time (see Chapter 12, Randomization Visit).

10.4.2.8.7 Pad Test Form

The person who distributes the Pad Test Kit must be PRIDE-certified. This should be the same person who completes the participant education procedures for the Pad Test including slide viewing, a review of the participant's Pad Test Kit materials and at-home participant procedures after slide viewing, completing the follow-up phone contact, etc.

1. **Date Pad Test Kit distributed:** Record the date you complete the participant education procedures and give the Pad Test Kit to the participant.
2. **Number of Pads in the Kit:** Record the total number of pads included in this participant's Pad Test Kit.
3. **Date pre-weights are recorded:** Record the date when the pre-weight measurements were done. Note that this is usually before the date of the visit.
4. **Pad #:** Record in sequential order, the number assigned to each pad included in the Kit. If 4 pads are included in the kit, record the number 1 in the field A, record the number 2 in the field B and so on. **Pre-weight:** Weigh each Pad following procedures described in Appendix 10F. For each pad included in the Kit, record the pad weight in grams to the nearest .01-gram weight.

No other data can be recorded until the participant returns with the Pad Test Kit and the Voiding Diary.

5. **Date post-weights are recorded:** Record the date when post-

weight measurements are documented on the Data Form.

6. **Post-weight:** Weigh each used pad following procedures described in Appendix 10F. Record the pad weight in grams to the .01-gram weight.
7. **Contamination Code:** Review the Pad Test Record Sheet and confirm with the participant to determine and record a contamination code.
8. **Other codes:** Do not weigh unused pads; leave the gram weight boxes blank.
 - If the pad is missing but not used, according to the participant, leave the gram weight boxes blank and enter "10" as the contamination code.
 - If the pad was returned but not used, enter "11" as the contamination code for that pad.
 - **If the pad is missing and the participant reports that she *did* use it, the test is invalid and should be repeated.** It is very important that all used pads be weighed. In this case, do not complete or fax this form; write "Invalid Test" across the form and file it in the participant's binder. Prepare another Pad Test Kit for the participant and print out a new Pad Test form. When a pad is missing but has been used the participant should not be randomized until the test has been repeated. At a follow-up visit, if the participant refuses to repeat the Pad Test, leave the gram weight boxes (beside the missing used pad) blank on the original Pad Test form and enter 12 for the contamination code. Fax the form as usual.

Contamination Codes: Record the appropriate code for each used pad.

Code	Description
Record 01	if the pad is not contaminated with anything other than urine.
Record 02	if the pad is soaked through with urine.
Record 03	if the pad is contaminated with blood.
Record 04	if the pad is contaminated with stool.
Record 05	if the pad is contaminated with blood and stool.

- Record 06 if the pad is soaked through with urine **and** contaminated with blood.
- Record 07 if the pad is soaked through with urine **and** contaminated with stool.
- Record 08 if the pad is soaked through with urine **and** contaminated with blood **and** stool.
- Record 09 if you cannot identify the contaminant.

If Kits are returned with some pads missing:

OTHER CODES

- Record 10 if the pad is missing and the participant reports that she **DID NOT USE** the pad during the 24-hour testing period.
- Record 11 if the pad is returned and **NOT USED**.
- Record 12 if the pad is missing and the participant reports that she **DID USE** the pad during the 24-hour testing period. This error will invalidate the test and the test should be repeated. Refer to the Operations Manual or call the CC for directions.

9. **Date Kit Returned:** Record the date the Pad Test Kit is returned. This should be the same date as the date the post-weight measurements are completed.

10.4.2.9 7-Day Voiding Diary (Number 2)

Follow the instructions in Section 9.3.3 for distribution and explanation of the 7-Day Voiding Diary. Note that the participant should complete the 24-Hour Pad test during days 4 – 7 of this Voiding Diary.

10.5 PRESENTING THE URODYNAMIC SUB-STUDY

A subgroup of 100 women (50 at each site) will have the opportunity to participate in the Urodynamic Sub-study (UDS). The UDS includes a standardized pelvic floor evaluation and urodynamic studies at baseline and at 6 months to elucidate the mechanism by which weight loss improves incontinence. This study is designed to (1) evaluate whether baseline urodynamic measures can identify women who are most

likely to experience improved continence after weight reduction and;
(2) examine the relationship of improvement in continence and changes in urodynamic measures.

All women who are eligible for PRIDE are eligible for the UDS but only the first 50 at each site who agree, will be randomized. The UDS visits are in addition to all regular visits for PRIDE.

Study personnel who discuss the UDS with participants should prepare by reading the UDS Protocol in Chapter 1 and the UDS procedures described in Chapter 11. The participant may be invited to watch the UDS informational slide presentation in addition to discussing the sub-study with PRIDE staff. A separate consent form and HIPPA authorization must be signed to participate in the sub-study. After 100 participants have had baseline UDS testing, the sub-study will no longer be presented as an option to women enrolling in PRIDE.

In order to minimize any bias of the main trial, participants in the sub-study will not be given their personal results until the end of the trial.

Once agreement to participate has been obtained, schedule the UDS visit by contacting the UDS study nurse according to local procedures. The UDS nurse will contact the participant, explain the procedures in more detail and arrange for the baseline UDS visit. Informed Consent for the Urodynamic Sub-Study will be reviewed and signed at the urogynecology site prior to the start of the UDS visit.

10.6 SCHEDULING THE RANDOMIZATION VISIT

The Randomization Visit should take place within 4 weeks of SV2.

Participants who are still eligible should leave the clinic with the following items:

- An appointment for the randomization visit
- 7-Day Voiding Diary #2
- 24-hour Pad Test Kit

10.7 SCREENING FORMS/Inclusion/Exclusion

At the end of each screening visit all the forms that have been collected or completed at that visit should be reviewed, and then faxed to the Coordinating Center data system. The Screening Visit checklist should be completed and faxed after Screening Visit 2 or at the time the participant is found to be ineligible.

The Inclusion/Exclusion form should be used during screening only to indicate that a participant has become ineligible for the study. For example, if the participant is found to be ineligible at SV1, then mark the one main reason and fax the Inclusion/Exclusion form at that time.

APPENDIX 10A
HOW TO COLLECT CLEAN URINE SAMPLE

How to collect a clean urine sample

6 easy steps for a clean sample

1. Wash and dry your hands thoroughly.
2. Remove the container cap and set it aside. Do not touch inner surfaces of container.
3. Wash your urogenital area with the towelette provided; wipe from front to back between the folds of skin.
4. Hold the lips of the vagina apart and begin urinating. Do not collect the first bit of urine you pass as this may be contaminated with bacteria from your skin or vaginal fluid. Let a small amount of urine pass into the toilet, then midway through, urinate into the container.
5. Replace the cap and tighten firmly.
6. Remember to wash your hands thoroughly after collecting the specimen.

APPENDIX 10B
Body Mass Index Table

BMI	Height(cm)																									
Weight kg.	150	154	154	156	158	160	162	164	166	168	170	172	174	176	178	180	182	184	186	188	190	192	194	196	198	200
60	27	26	25	24	24	23	23	22	22	21	21	20	20	19	19	18	18	17	17	17	16	16	16	15	15	15
62	28	27	26	26	25	24	24	23	22	22	21	21	20	20	19	19	19	18	18	17	17	16	16	16	16	15
64	28	28	27	26	26	25	24	24	23	22	22	22	21	21	20	19	19	19	18	18	17	17	17	16	16	16
66	29	29	28	27	26	26	25	24	24	23	23	22	22	21	21	20	20	19	19	18	18	17	17	17	17	16
68	30	30	29	28	27	26	26	25	25	24	23	23	22	22	21	21	20	20	19	19	19	18	18	17	17	17
70	31	30	30	29	28	27	27	26	25	25	24	24	23	23	22	21	21	20	20	20	19	18	18	18	18	17
72	32	31	30	30	29	28	27	27	26	25	25	24	24	23	23	22	22	21	20	20	20	19	19	18	18	18
74	33	32	31	30	30	29	28	27	27	26	26	25	24	24	23	23	22	22	21	21	20	20	20	19	19	19
76	34	33	32	31	30	30	29	28	27	27	26	26	25	24	24	23	23	22	22	21	21	20	20	20	19	19
78	35	34	33	32	31	30	30	29	28	27	27	26	26	25	24	24	23	23	22	22	21	21	21	20	20	19
80	36	35	34	33	32	31	30	30	29	28	27	27	26	26	25	24	24	23	23	22	22	22	21	21	20	20
82	36	36	35	34	33	32	31	30	30	29	28	27	27	26	26	25	25	24	23	23	22	22	22	21	21	20
84	37	37	35	35	34	33	32	31	30	30	29	28	28	27	26	26	25	25	24	23	23	22	22	22	21	21
86	38	37	36	35	34	34	33	32	31	30	30	29	28	28	27	26	26	25	25	24	23	23	23	22	22	21
88	39	38	37	36	35	34	33	32	31	30	30	29	28	28	27	26	26	25	25	24	23	23	23	22	22	21
90	40	39	38	37	36	35	34	33	33	32	31	30	30	29	28	28	27	26	26	25	25	24	24	23	23	22
92	41	40	39	38	37	36	35	34	33	33	32	31	30	30	29	28	28	27	26	26	25	25	24	24	23	23
94	42	41	40	39	38	37	36	35	34	33	32	32	31	30	30	29	28	28	27	26	26	25	25	24	24	23
96	43	42	41	40	38	38	37	36	35	34	33	32	32	31	30	30	29	28	28	27	26	26	25	25	24	24
98	44	43	41	40	39	38	37	36	35	35	34	33	32	32	31	30	30	29	28	28	27	26	26	25	25	24
100	44	43	42	41	40	39	38	37	36	35	35	34	33	32	32	31	30	29	29	28	28	27	26	26	25	25
102	45	44	43	42	41	40	39	38	37	36	35	34	34	33	32	31	31	30	29	29	28	28	27	26	26	25
104	46	45	44	43	42	41	40	39	38	37	36	35	34	34	33	32	31	31	30	29	29	28	28	27	26	26
106	47	46	45	44	42	41	41	39	38	38	37	36	35	34	33	33	32	31	31	30	29	29	28	28	27	26
108	48	47	46	44	43	42	41	40	39	38	37	36	36	35	34	33	33	32	31	31	30	29	29	28	28	27
110	49	48	46	45	44	43	42	41	40	39	38	37	36	35	35	34	33	32	32	31	31	30	29	29	28	28
110 +	49+	48+	46+	45	44	43	42	41	40	39	38	37	36	35	35	34	33	32	32	31	31	31	29	29	28	28

BMI	Height(in)																		
	58	59	60	61	62	63	64	65	66	67	68	69	70	71	72	73	74	75	76
Weight (lbs)	4'10"	4'11"	5'0"	5'1"	5'2"	5'3"	5'4"	5'5"	5'6"	5'7"	5'8"	5'9"	5'10"	5'11"	6'0"	6'1"	6'2"	6'3"	6'4"
100	21	20	20	19	18	18	17	17	16	16	15	15	14	14	14	13	13	13	12
105	22	21	21	20	19	19	18	18	17	16	16	16	15	15	14	14	14	13	13
110	23	22	22	21	20	20	19	18	18	17	17	16	16	15	15	15	14	14	13
115	24	23	23	22	21	20	20	19	19	18	18	17	17	16	16	15	15	14	14
120	25	24	23	23	22	21	21	20	19	19	18	18	17	17	16	16	15	15	15
125	26	25	24	24	23	22	22	21	20	20	19	18	18	17	17	17	16	16	15
130	27	26	25	25	24	23	22	22	21	20	20	19	19	18	18	17	17	16	16
135	28	27	26	26	25	24	23	23	22	21	21	20	19	19	18	18	17	17	16
140	29	28	27	27	26	25	24	23	23	22	21	21	20	20	19	19	18	18	17
145	30	29	28	27	27	26	25	24	23	23	22	21	21	20	20	19	19	18	18
150	31	30	29	28	27	27	26	25	24	24	23	22	22	21	20	20	19	19	18
155	32	31	30	29	28	28	27	26	25	24	24	23	22	22	21	20	20	19	19
160	34	32	31	30	29	28	28	27	26	25	24	24	23	22	22	21	21	20	20
165	35	33	32	31	30	29	28	28	27	26	25	24	24	23	22	22	21	21	20
170	36	34	33	32	31	30	29	28	27	27	26	25	24	24	23	22	22	21	21
175	37	35	34	33	32	31	30	29	28	27	27	26	25	24	24	23	23	22	21
180	38	36	35	34	33	32	31	30	29	28	27	27	26	25	24	24	23	23	22
185	39	37	36	35	34	33	32	31	30	29	28	27	27	26	25	24	24	23	23
190	40	38	37	36	35	34	33	32	31	30	29	28	27	27	26	25	24	24	23
195	41	39	38	37	36	35	34	33	32	31	30	29	28	27	27	26	25	24	24
200	42	40	39	38	37	36	34	33	32	31	30	30	29	28	27	26	26	25	24
205	43	41	40	39	38	36	35	34	33	32	31	30	29	29	28	27	26	26	25
210	44	43	41	40	38	37	36	35	34	33	32	31	30	29	29	28	27	26	26
215	45	44	42	41	39	38	37	36	35	34	33	32	31	30	29	28	28	27	26
220	46	45	43	42	40	39	38	37	36	35	34	33	32	31	30	29	28	28	27
225	47	46	44	43	41	40	39	38	36	35	34	33	32	31	31	30	29	28	27
230	48	47	45	44	42	41	40	38	37	36	35	34	33	32	31	30	30	29	28
235	49	48	46	44	43	42	40	39	38	37	36	35	34	33	32	31	30	29	29
240	50	49	47	45	44	43	41	40	39	38	37	36	35	34	33	32	31	30	29
245	51	50	48	46	45	43	42	41	40	38	37	36	35	34	33	32	32	31	30
250	52	51	49	47	46	44	43	42	40	39	38	37	36	35	34	33	32	31	30
255	53	52	50	48	47	45	44	43	41	40	39	38	37	36	35	34	33	32	31
260	54	53	51	49	48	46	45	43	42	41	40	38	37	36	35	34	33	33	32
265	56	54	52	50	49	47	46	44	43	42	40	39	38	37	36	35	34	33	32
270	57	55	53	51	49	48	46	45	44	42	41	40	39	38	37	36	35	34	33
275	58	56	54	52	50	49	47	46	44	43	42	41	40	38	37	36	35	34	34
280	59	57	55	53	51	50	48	47	45	44	43	41	40	39	38	37	36	35	34
285	60	58	56	54	52	51	49	48	46	45	43	42	41	40	39	38	37	36	35
290	61	59	57	55	53	51	50	48	47	46	44	43	42	41	39	38	37	36	35
295	62	60	58	56	54	52	51	49	48	46	45	44	42	41	40	39	38	37	36
300	63	61	59	57	55	53	52	50	49	47	46	44	43	42	41	40	39	38	37

APPENDIX 10C HEALTH HISTORY

Participant ID #	Acrostic	Date of Visit	Staff ID #
 13658 		 /  /  <small>Month Day Year</small>	

HEALTH HISTORY
(Self-Administered)

Visit: Screening

16. Has a doctor ever told you that you had, or currently have, any of the following conditions or diseases?
- a. A fistula or a hole in your bladder, rectum or near there?
- Yes → **NOT ELIGIBLE**
 No
 Don't Know
- b. A birth defect leading to urine leakage?
- Yes → **NOT ELIGIBLE**
 No
 Don't Know
- c. Urine leakage starting in childhood?
- Yes → **NOT ELIGIBLE**
 No
 Don't Know
- d. Interstitial cystitis or very painful bladder?
- Yes → **NOT ELIGIBLE**
 No
 Don't Know
- e. Problems with your spinal cord or back leading to urine leakage?
- Yes → **NOT ELIGIBLE**
 No
 Don't Know

Participant ID #	Acrostic	Date of Visit			Staff ID #
    	    	 /  /   	  	  	  
		Month	Day	Year	

HEALTH HISTORY (Self-Administered)

Visit: Screening

16. (Continued)
Has a doctor ever told you that you had, or currently have, any of the following conditions or diseases?
- f. Multiple sclerosis?
- Yes → **NOT ELIGIBLE**
- No
- Don't Know
- g. Parkinson's disease?
- Yes → **NOT ELIGIBLE**
- No
- Don't Know
17. Has a health care provider ever told you that you had, or currently have, hypertension?
- Yes → If BP is $\geq 160/100$ at RV, participant is **NOT ELIGIBLE**
- No
18. Has a health care provider ever told you that you had, or currently have, high cholesterol?
- Yes → Requires MD approval
- No
19. Has a health care provider ever told you that you had, or currently have, coronary heart disease?
- Yes
- No

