6.3 Exclusion Criteria

1. current use, or use within the previous month*, of medical therapy for incontinence or weight loss
2. pregnant or gave birth in the previous 6 months
3. urinary tract infection (dipstick urinalysis positive for leukocyte esterase, nitrites or blood) or report having ≥ 4 urinary tract infections in the preceding year
4. incontinence of neurologic or functional origin (by history)
5. report prior anti-incontinence or urethral surgery, pelvic cancer or pelvic irradiation
6. report significant medical conditions of the genitourinary tract (genitourinary fistula, interstitial cystitis, symptomatic pelvic organ prolapse)
7. report a medical condition that would affect the safety and/or efficacy of a weight management program involving diet and physical activity, including type 2 diabetes requiring medical therapy that may cause hypoglycemia, chronic steroid use or uncontrolled hypertension (systolic blood pressure >180 mm Hg or diastolic blood pressure > 100 mm Hg); women with a history of coronary heart disease may participate with written approval from their primary care physician
8. engaged in an active weight loss program and/or experienced a weight reduction of 10 lbs or more in the past 3 months
9. report conditions that, in the judgment of the clinical center Principal Investigator, render potential participants unlikely to follow the protocol for 18 months, including illness likely to be terminal within 2 years, plans to move, substance abuse, significant psychiatric problems, or dementia
10. participating in another research study that involves investigational drugs or can potentially confound the results of PRIDE

* Potential participants may be re-screened one month after stopping medical therapy for incontinence or obesity. Prior medical therapy for incontinence or obesity will not affect eligibility but participants will be asked not to initiate any

treatment for incontinence or obesity during the study period except as directed by the study protocol.

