10.3.6 Health History

The health history is a self-administered questionnaire that should be filled out by the participant during the clinic visit and checked by study staff before the participant leaves the clinic. Review the form for missing responses, for completion of sub-category questions (e.g. if #2 is answered “yes” then 2a should be completed) and for information that affects eligibility. **There are some important exclusion criteria contained in the health history.** An interviewer-annotated version of this form that highlights the eligibility questions is attached as Appendix 10C.

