In this case, mark the Inclusion/Exclusion form as follows: If the participant responds “Yes” to 16a, 16b, 16c, or 16d, then mark “Yes” for Exclusion Criteria, item G. If the participant responds “Yes” to 16e, 16f or 16g, then mark “Yes” for Exclusion Criteria, item E. If the participant marks “don’t know” to any of the questions 16a to 16g she is still eligible to continue screening.

Questions 17. This question probes for a history of hypertension. A “yes” response does not exclude the participant. Blood pressure will be measured during screening to determine eligibility.

Question 18. High cholesterol does not exclude the participant.

Question 19. If the participant has a history of coronary heart disease she is not excluded from PRIDE, but she must obtain approval from her health care provider in order to participate in PRIDE. Please confirm that she has obtained a letter and make sure the letter is filed in her study binder prior to the Randomization Visit.

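### The annotated Health History (Appendix 10C) shows the physician-approval note at question 18 (high cholesterol) and none at question 19 (coronary heart disease), contrary to the protocol and the manual's own instructions

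*Protocol*

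**What the plan says.** Operations Manual 10.3.6 has staff check the self-administered Health History before the participant leaves the clinic and points them to an aid: "An interviewer-annotated version of this form that highlights the eligibility questions is attached as Appendix 10C". The Chapter 10 contents list describes that appendix as covering questions 16 to 19.

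In Appendix 10C the Yes answer to question 18 (high cholesterol) reads "Yes → Requires MD approval". Question 19 asks "Has a health care provider ever told you that you had, or currently have, coronary heart disease" and is followed by plain Yes and No options with no note.

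The instructions for the same form, in manual 10.3.6.1, read differently. For cholesterol: "Question 18. High cholesterol does not exclude the participant", with no mention of approval. For coronary heart disease: "she must obtain approval from her health care provider in order to participate in PRIDE", followed by "Please confirm that she has obtained a letter and make sure the letter is filed in her study binder prior to the Randomization Visit".

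Protocol 6.3, item 7, states the entry rule: "women with a history of coronary heart disease may participate with written approval from their primary care physician". The wording is the same in the initial protocol and in the version carrying Amendment 5. Manual 8.3 requires a letter before enrolment for candidates with coronary heart disease, and 8.7.23 (telephone question 20e) requires permission and a tracking-log entry that a letter is due before randomization.

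**The concern.** Staff have two sets of instructions for reading the same form, and the two disagree on a safety-related entry condition. Someone working from the annotated page would ask a woman with raised cholesterol for an approval that no other passage mentions, and would see no prompt for a woman reporting coronary heart disease. Section 8.7.23 explains why approval is sought: although the exercise programme is not regarded as strenuous, a candidate may have been inactive for a long time. A missed prompt could therefore let a woman into the programme without the documentation the protocol asks for. The reverse error could delay or lose women who are otherwise eligible.

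**Working it through.** There is no arithmetic here. The check is a comparison of passages.

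**1. Which condition carries the approval?**

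| Place | High cholesterol | Coronary heart disease |
|---|---|---|
| Protocol 6.3, item 7 | not mentioned | written approval |
| Manual 8.3 | not mentioned | letter before enrolling |
| Manual 8.7.23 (telephone question 20e) | not mentioned | permission, letter logged as expected |
| Manual 10.3.6.1 (questions 18 and 19) | does not exclude, no approval | approval, letter filed before randomization |
| Appendix 10C | approval note | no note |

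The first four differ slightly in who may sign (primary care physician, health care provider, or cardiologist) but agree on the condition. Appendix 10C is the only one that differs on the condition.

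**2. Could the note have moved when the page was converted to text?** The form carries nine notes: one each for 16a to 16g (seven), one for 17, and one for 18. The seven on question 16 match 10.3.6.1, where a Yes to any of them excludes. The note on question 17 concerns blood pressure and sits on the hypertension question. So eight of the nine are on the question they belong to. This makes a shift of the ninth alone less likely but does not rule it out.

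**3. What else would catch a woman with heart disease?**
- Before the Health History: telephone questions 20a to 20d ask about the relevant conditions, 20e asks whether she will obtain written approval, and staff note on the tracking log that a letter is due.
- At the Health History: the question 19 instruction in 10.3.6.1 tells staff to confirm and file the letter.
- At randomization: exclusion item H in Appendix 12A asks about any medical condition affecting safety and lists the Eligibility Screening Form and the Health History among its sources. It gives type 2 diabetes and uncontrolled hypertension as examples and does not name coronary heart disease or the letter. No other item in Appendix 12A does so.
- On delayed schedules: manual 4.3 allows up to 9 months from eligibility screening to randomization. Where Screening Visit 1 and randomization are more than 3 months apart, the part B table in Appendix 9B re-checks new diagnoses through Eligibility Screening questions 8, 15, 19 and 21 to 26 and Health History 16a to 16g. It leaves out Eligibility Screening question 20 and Health History question 19. (Part A reviews the whole Eligibility Screening Form, but only for a long gap before the Orientation Visit.)

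**4. Who is left exposed?** A woman who was not identified at telephone question 20, who first reports coronary heart disease at Health History question 19, and whose form is read by staff following Appendix 10C over 10.3.6.1. For her, the question-specific prompt is one sentence in 10.3.6.1, which the annotated page contradicts.

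**The case against.** The strongest reply is that this may be no error in the manual at all. Appendix 10C is a scanned-style form page whose annotations were added to a participant questionnaire, and extracted text cannot establish layout. All the other passages put the approval on heart disease, so a note displaced by one question is a live explanation. That stands as a reason to look at the original page before calling it a misprint. It does not dispose of the point, since the other eight notes came through on their own questions.

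The second reply is that Appendix 10C is an aid and not the sole control. This also stands, and it limits the consequence. A reader might infer that any woman with heart disease can enter the exercise programme without approval, or that every participant is affected at her first Health History. The documents do not support either reading: telephone question 20, the tracking log, section 8.3 and the question 19 instruction all still require the letter. The visit schedule in Protocol 8.1 also lists physician consent at the screening visits, though it does not say for which women.

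A reader might also multiply an assumed prevalence of heart disease or raised cholesterol by 330. That would count everyone with the condition, not the few who pass the telephone screen unidentified and are then handled from the annotation alone. Nor do the documents show the same fault in a website copy. Section 8.7 describes the annotated version there as covering questions 16 and 17, which are not in dispute.

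**Conclusion.** The contradiction is real in the text supplied: Appendix 10C disagrees with Protocol 6.3 and with manual 8.3, 8.7.23 and 10.3.6.1 on which answer calls for physician approval. It is a wrong or displaced eligibility annotation, with no bearing on the trial's design, sample size or analysis. The exposed group is limited to women who first declare heart disease on the Health History and whose staff rely on the annotated page. Its size cannot be estimated from the documents. The point is still worth correcting because, for those women, neither the final checklist nor the part B re-check prompts for the letter. The conclusion assumes that the text reflects the printed page, which has not been verified.

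**What to change.** First compare the text with the original Appendix 10C page. If the note is printed beside question 19, nothing needs changing. If it is printed beside question 18, Appendix 10C must be reconciled with Protocol 6.3 (item 7) and manual 8.3, 8.7.23 and 10.3.6.1, and the page reissued to both sites. In that case also check, for each randomized woman who answered Yes to Health History question 19, that the documentation those passages require is on file. The cost is one form page and a file check, with no change to randomization, outcomes or analysis.
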